15.3.1 Symptomatic Venous Thromboembolism

The proportion of subjects who develop symptomatic VTE within 24 months post-randomization (subdivided according to whether the event was within the first 10 days, 11 to 30 days, 31 to 90 days, or 91 days to 24 months) will be compared between the two treatment groups using a stratum-adjusted Cochran-Mantel-Haenszel test.

15.3.2 Major and Any Bleeding

The proportion of subjects with major bleeding during the 10 days after randomization, and between 11 days and 24 months, will be compared between the two groups using a stratum-adjusted Cochran-Mantel-Haenszel test. A similar comparison will be undertaken for any bleeding (major or minor). The nature of major bleeds (e.g. intracranial, needing surgery or transfusion) will be described. Complications will also be described by outcome according to SIR reporting standards (48,120).

15.3.3 Deaths

Overall and cause-specific counts of death will be described in the two treatment groups; the overall mortality at 1 month and 24 months will be compared using a stratum-adjusted Cochran-Mantel-Haenszel test. In addition, Kaplan-Meier curves will be estimated for the two treatment arms.

15.3.4 Disease-Specific Quality of Life

The change in VEINES-QOL and VEINES-Sym scores from baseline to 24 months will be compared between the two groups using a Student's t-test (for each scale, a difference of 4

points is clinically meaningful). A linear mixed model analysis of the repeated assessments (at 1, 6, 12, 18 and 24 months) with baseline scores as a covariate will be used to investigate the changes over time, and if they differ by treatment arm.

15.3.5 Generic Quality of Life

The change in SF-36v2 PCS and MCS scores from baseline to 24 months will be compared between the two groups using a Student's t-test. A difference of 5 points on each scale is considered to be clinically relevant. In addition, a linear mixed model analysis of the repeated assessments (at 1, 6, 12, 18 and 24 months) with baseline scores as a covariate will be used to investigate the changes over time, and if they differ by treatment arm.

15.3.6 Severity of Post-Thrombotic Syndrome

Villalta severity classification (none, mild, moderate, severe) at 24 months will be compared between the two arms (4 x 2 table) using an exact Kruskal-Wallis nonparametric test with severity as a single ordered factor. In addition, ordinal logistic regression analysis adjusting for baseline factors will be performed. We will also use a linear mixed model for the repeated total Villalta scores (assessed at 10 days and 1, 6, 12, 18, and 24 months) with the baseline score serving as a covariate, to investigate their response patterns over time, and assess if they differ by treatment arm. In addition, the proportion of patients with either moderate or severe PTS will be compared between the two treatment groups using a stratum-adjusted Cochran-Mantel-Haenszel test. The CEAP Clinical Class and VCSS scores will be similarly analyzed.

15.3.7 Major Non-PTS Treatment Failure and Composite Outcome

The proportion of subjects who experience a major non-PTS treatment failure, defined as meeting one or more of the following criteria, will be reported for the two treatment arms:

- (1) the subject undergoes an unplanned endovascular or surgical intervention for the treatment of severe symptomatic venous disease in the index leg within the first 6 months after randomization (excluding PCDT Arm patients who undergo repeat PCDT within the first 3 months after randomization, and Control Arm patients whose intervention occurs within 7 days post-randomization and was not prompted by acute limb-threatening circulatory compromise);
- (2) the subject undergoes an amputation in the index leg anytime within 24 months after randomization; and/or
- (3) the subject develops venous gangrene in the index leg within the first 6 months after randomization.

The composite sum of the proportions of subjects who either develop PTS or experience a major non-PTS treatment failure during 24 months of follow-up will be compared between the two treatment arms using a stratum-adjusted Cochran-Mantel-Haenszel test.

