6.2.8 Crossover, Re-Treatment with PCDT, and Use of Other Endovascular Interventions

Experimental Arm subjects who develop symptomatic acute re-thrombosis in the iliac, common femoral, and/or femoral vein of the treated limb within the first 3 months after randomization may be re-treated with PCDT using the methods described in this protocol, if re-treatment would be consistent with the physician's standard practice and the patient's wishes. To be eligible for such re-treatment with PCDT, the patient's clinical presentation should be consistent with an acute re-thrombosis occurring within the last 14 days. Prior to re-treatment, the patient's clinical status should be re-evaluated. Re-treatment with PCDT should not be performed if the patient meets any one (or more) of the following Exclusion Criteria (Section 4.3): #6, 7, 8, 9, 10, 11, 12, 13, 15, 16, 18, or 20. No more than two re-treatments should be performed in any patient. Any planned deviation from these guidelines should first be discussed with the Principal Investigator.

In all other situations (i.e. Experimental Arm subjects beyond 3 months after randomization, and Control Arm subjects anytime), the use of PCDT is strongly discouraged in the absence of limb-threatening circulatory compromise. If a Control Arm subject is judged to require PCDT, the Principal Investigator should be notified before PCDT is performed to ensure that this decision is adequately justified and documented. During follow-up, the use of other endovascular treatments (e.g. iliac vein stent placement as a stand- alone treatment) is strongly discouraged in all subjects absent a compelling indication.

Subjects in either treatment Arm who require endovascular intervention for treatment of severe symptomatic venous disease in the index leg during follow-up (except Experimental Arm patients being re- treated with PCDT within the first 3 months after randomization) will be asked to undergo a standardized clinical assessment for PTS (Section 8.9) before being treated. If the intervention is performed more than 6 months post-randomization, then the findings of this assessment will be used in evaluating whether the subject has PTS for the final analysis, per the guidelines in Sections 15.2 and 15.3.7. If this clinical assessment cannot be done, subjects who undergo an endovascular venous intervention in the index leg more than 6 months post-

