8.2 Secondary Efficacy Outcomes

- PTS occurrence at 6, 12 and 18 months, assessed using Villalta PTS Scale (as above).
- Major non-PTS treatment failure during 24 months (see Section 15.3.7 for definition)
- Composite of PTS occurrence + major non-PTS treatment failure during 24 months
- PTS severity at 6, 12, 18 and 24 months, assessed using:
 - a) Villalta PTS Scale
 - b) Venous Clinical Severity Score (VCSS)
 - c) Clinical Class in the Clinical-Etiologic-Anatomic-Pathophysiologic (CEAP) System.
- Quality of Life (QOL) at 1, 6, 12, 18 and 24 months, assessed using:
 - a) SF-36v2 measure (general QOL)
 - b) VEINES-QOL/Sym measure (venous disease-specific QOL).
- Resolution of leg pain at 10 days and 1 month, assessed using Likert scale scores.
- Resolution of leg swelling at 10 days and 1 month, assessed using standardized measurement of calf circumferences.
- Degree of clot lysis with PCDT, assessed venographically (Experimental Arm only).
- Prevalence of valvular reflux and residual thrombus at 1 year (Duplex ultrasound).
- Cost-effectiveness, measured in dollars per quality-adjusted life-year (QALY).

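### Criterion (1) of major non-PTS treatment failure depends on the arm, so the secondary composite can favour PCDT by definition alone

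*Protocol*

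**What the plan says.** Section 8.2 lists major non-PTS treatment failure, and the "Composite of PTS occurrence + major non-PTS treatment failure during 24 months", among the secondary efficacy outcomes.

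Criterion (1) in Section 15.3.7 runs for half a year from randomization. Its event is worded as follows, the last figure being in months: "the subject undergoes an unplanned endovascular or surgical intervention for the treatment of severe symptomatic venous disease in the index leg within the first 6". Two exemptions follow, one per arm:

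- PCDT arm: "excluding PCDT Arm patients who undergo repeat PCDT within the first 3 months after randomization".
- Control arm: "Control Arm patients whose intervention occurs within 7 days post-randomization and was not prompted by acute limb-threatening circulatory compromise".

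Criteria (2) and (3), amputation and venous gangrene, do not mention the arm. The failure proportion itself is only reported. The composite is tested: subjects who "develop PTS or experience a major non-PTS treatment failure during 24 months of follow-up will be compared between the two treatment arms", by a stratum-adjusted Cochran-Mantel-Haenszel (CMH) test. Section 15.3 sets the secondary threshold at a two-sided 0.01. The same sentence describes the composite as "The composite sum of the proportions of subjects who either develop PTS or experience a major non-PTS treatment failure".

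Section 6.2.8 shows where the PCDT-arm exemption comes from. It permits re-treatment in the first 3 months for "Experimental Arm subjects who develop symptomatic acute re-thrombosis in the iliac, common femoral, and/or femoral vein of the treated limb". For controls it strongly discourages PCDT at any time unless there is limb threat. Its list of exclusion criteria that bar re-treatment leaves out criterion 5, limb-threatening circulatory compromise.

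**The concern.** An endpoint compared between randomized arms should be scorable without knowing the arm. Criterion (1) is not: the same clinical history can be a failure in one arm and not in the other. A control who has PCDT on day 30 fails, and a PCDT patient re-treated with PCDT on day 30 does not. The limb-threat qualifier narrows only the control exemption. A control treated on day 5 for limb threat fails, while a PCDT patient re-treated on day 30 for limb threat does not, and Section 6.2.8 does not rule that re-treatment out.

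At stake is the reading of one formally tested secondary efficacy outcome. Part of any composite difference in favour of PCDT could come from the scoring rule and not from how patients fared.

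**Working it through.** **Step 1. The two rules side by side.** Scoring under criterion (1), for an unplanned index-leg intervention for severe symptomatic venous disease:

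| Period and event | Control | PCDT arm |
|---|---|---|
| Days 0-7, PCDT (repeat PCDT in the PCDT arm), no limb threat | exempt | exempt |
| Days 0-7, PCDT (repeat PCDT in the PCDT arm), limb threat | failure | exempt |
| Days 0-7, other intervention, no limb threat | exempt | failure |
| Days 0-7, other intervention, limb threat | failure | failure |
| Day 8 to month 3, PCDT (repeat PCDT in the PCDT arm) | failure | exempt |
| Day 8 to month 3, other intervention | failure | failure |
| Months 3-6, any intervention | failure | failure |

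Three rows differ. Two work against controls, including the one covering nearly the whole 3 months. One works against the PCDT arm, in the first week only.

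**Step 2. The protocol's own figure.** Section 15.1 gives no calculation for the composite. Its primary calculation reproduces. For 30% v 20% at two-sided 0.05, exact Fisher power at 311 per arm is 80.0%. With 10% loss, 311/0.9 = 345.6, so 346 per arm and 692 in total.

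**Step 3. Size of the artificial difference.**

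Inputs:
- base composite rate b = 30% in both arms (the control PTS rate in Section 15.1, used as a stand-in), and 20% as a second case;
- n = 311 per arm (Section 15.1);
- alpha = 0.01 two-sided (Section 15.3);
- q = share of each arm with a day 8 to month 3 PCDT and no other composite component. **This is an assumption.** The protocol gives no rate, so a range of 0.5% to 8% is shown.

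With identical true outcomes, the counted rates are p_C = b + q and p_E = b, so the false difference is q. The CMH test is approximated by an unstratified two-proportion test:

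- SE0 = sqrt(2 × pbar × (1 - pbar)/n), with pbar = (p_C + p_E)/2
- SE = sqrt([p_C(1 - p_C) + p_E(1 - p_E)]/n)
- rejection = 1 - Φ((2.576 × SE0 - q)/SE) + Φ((-2.576 × SE0 - q)/SE)

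For b = 30% and q = 5%:
- SE0 = sqrt(2 × 0.325 × 0.675/311) = 0.03756
- SE = sqrt((0.2275 + 0.2100)/311) = 0.03751
- upper term: (2.576 × 0.03756 - 0.05)/0.03751 = 1.246, giving 10.6%; the lower term is negligible.

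| q (assumed) | Counted composite at b = 30%, control v PCDT | Two-sided type I error at nominal 1%, b = 30% | Same, b = 20% |
|---|---|---|---|
| 0.5% | 30.5% v 30% | 1.07% | 1.09% |
| 1% | 31% v 30% | 1.28% | 1.36% |
| 2% | 32% v 30% | 2.17% | 2.55% |
| 3% | 33% v 30% | 3.86% | 4.81% |
| 5% | 35% v 30% | 10.64% | 13.91% |
| 8% | 38% v 30% | 31.86% | 40.48% |

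Almost all of the excess is false findings for PCDT. In that direction the nominal rate is 0.5%, and it becomes 1.1%, 3.8% and 10.6% at q = 1%, 3% and 5% (b = 30%).

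q is smaller than the overall early intervention rate, because some of these subjects also develop PTS. If the two were independent, a 5% overall rate would give q = 0.05 × 0.70 = 3.5%.

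**Step 4. With one rule for both arms.** Counting or exempting the same events over the same window makes the artificial difference 0 at equal true rates, and the test keeps its 1% level.

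**The case against.** The asymmetry is disclosed and looks deliberate. Section 6.2.8 makes re-treatment to 3 months part of the experimental strategy, within limits, while PCDT in a control departs from assigned therapy. On that view the two events are not the same. Criterion (1) also counts procedures and not disease. If one arm may be re-treated and the other is discouraged from treatment, an arm-neutral count partly measures permission and could count more PCDT-arm failures at identical re-thrombosis rates. This stands: which definition should lead is open to debate, and the neutral version is not free of bias. It does not justify resting a between-arm claim on the arm-specific version alone.

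The size may also be small. Sections 6.2.8 and 12.4 are written to keep control PCDT rare, and at a 1% rate the type I error is 1.3%. This stands too. The offsets in Step 1 are real: the control 7-day exemption covers every intervention type, and non-PCDT interventions in the PCDT arm always count.

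A reader might go further and infer three things that the protocol does not support:

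- **That re-thrombosis after PCDT is hidden.** Section 9.3 distinguishes early re-thrombosis of treated segments. Section 15.3.1 compares symptomatic VTE between arms, subdivided at 10, 30 and 90 days. Re-treated subjects stay in follow-up, so later PTS still counts.
- **That the primary result is affected.** The rule in Section 15.2 for interventions after 6 months is the same in both arms.
- **That subjects with both components are counted twice.** The either/or wording and a CMH test imply one binary value per subject. The reference to a sum is loose wording.

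**Conclusion.** The point holds for the secondary composite. Criterion (1) is arm-specific, and at equal true rates this creates a difference favouring PCDT. That difference roughly equals the control-arm rate of day 8 to month 3 interventions in subjects with no other component. Strictly it is the PCDT part of that rate, since other interventions in that period count in both arms. Limb-threat PCDT in the first week adds slightly, and the first-week offset subtracts.

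The size cannot be derived from the protocol. It rests on an assumed rate, a 30% base rate, 311 per arm and an unstratified approximation: two-sided type I error of about 1.3%, 3.9% and 10.6% against a nominal 1%, at rates of 1%, 3% and 5%. At 1% or below the inflation is minor. With one secondary outcome affected and the primary untouched, this should be fixed but does not undermine the trial.

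**What to change.** 1. Define criterion (1) with the same window, intervention types and limb-threat qualifier in both arms. One way is to count, in either arm, any unplanned endovascular or surgical intervention for severe symptomatic venous disease in the index leg from day 8 to month 6, plus any prompted by limb threat in the first 7 days.
2. Report the composite under both this definition and the present one. Do not conclude a PCDT benefit on the composite unless it holds under the arm-neutral version.
3. State that the arm-neutral count partly reflects the different re-treatment policies in Section 6.2.8.
4. As a wording clarification, describe the composite as the proportion of subjects with either component.

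The cost is about one paragraph in Section 15.3.7 or in the analysis plan foreseen in Section 15.6, plus one extra analysis. Later endovascular procedures already have a case report form (Section 6.1.2). The PCDT arm may look less favourable under the neutral count. No clinical re-treatment rule changes.

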15.3.8 Inter-Relationship between Scales

The relationships between VEINES-QOL, SF-36v2 PCS and MCS scores, Villalta score, CEAP, and VCSS will be explored using multivariate methods.

15.3.9 Residual Thrombosis after PCDT Correlated with PTS

Among Experimental Arm subjects, the extent of proximal DVT on venography after PCDT will be correlated with the presence of PTS at 24 months. For these analyses, extent of residual DVT will be considered as a continuous variable (Marder Score of 0 to 24) and PTS will be considered both as a continuous variable (Villalta score 0-33), and as a dichotomous variable (PTS present or absent). Analysis will include multivariable linear regression for the continuous outcome, and logistic regression for the binary outcome, adjusting for baseline variables.

15.3.10 Residual Thrombosis and Valvular Reflux Correlated with PTS

The extent of residual thrombosis (0-10) and venous reflux (0-10), and the total Venous Segmental Disease Score (0-20), will be described for the two groups, and will be compared (Student's t-test). These scores (total, and component parts) will be correlated with the presence and severity of PTS at 24 months using the techniques outlined in Section 15.3.8.

15.3.11 Resolution of Acute Symptoms

Mean absolute change in severity of leg pain, measured using a 7-point Likert scale, from baseline to 10 days and 1 month after randomization will be compared between the two arms using an analysis of co-variance. Leg circumference (measured and percentage change in leg circumference compared to pretreatment values), at 10 days and 1 month will be compared between the two arms using the Student's t-test. In the PCDT group, the mean change scores in leg pain and leg circumference will be correlated with degree of thrombus removal as assessed by mean change in Marder scores between pre-PCDT and post-PCDT venograms.

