8.11 Resolution of Leg Pain and Swelling

To determine if PCDT leads to faster DVT symptom resolution, the severity of pain in each leg will be assessed on a 7-point Likert scale at baseline and 10-day and 1-month follow-up. The subject will be asked to "Please rate the overall intensity of "pain" or "discomfort" that you have felt in your leg during the past 24 hours by checking one response on the following scale" (1 = No pain, 2 = Very mild pain, 3 = Mild pain, 4 = Moderate pain, 5 = Severe pain, 6 = Very severe pain, 7 = Extremely severe pain). Likert scales are widely validated for pain severity assessment (114,115). The Likert scale and accompanying instructions will be available in the originally validated English version and in a certified Spanish translation. Calf circumference 10cm below the tibial tuberosity will also be measured at baseline and 10-day and 1-month follow-up. At these visits, venous symptoms and signs will also be assessed using the Villalta PTS Scale. The clinician performing these assessments must be blinded to subject treatment allocation.

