15.3 Secondary Analyses

Secondary analyses will be performed using both analysis sets. To account for multiple testing, a two-sided p-value of 0.01 or less will be considered statistically significant for all tests (144).

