15.4 Additional Analysis Issues

15.4.1 Confounding

Stratification at randomization for the extent of DVT and Clinical Center and the standardization of the use of standard DVT therapy (Section 12.5) will reduce the potential for confounding. However, in addition to the unadjusted analysis described above, an adjusted analysis of the study outcomes comparing treatment Arms will be performed using multivariable regression analysis (linear regression for continuous outcomes, logistic regression for binary outcomes) that controls for the following baseline variables as main effects: age (continuous), gender (female vs. male), ethnicity (Hispanic/Latino vs. other), race (American Indian/Alaskan Native, Asian, Black, Hawaiian/Pacific Islander vs. White), body-mass index, employment status, previous ipsilateral DVT, inpatient (yes, no), duration of leg symptoms, extent of DVT at presentation (iliofemoral vs. femoropopliteal), symptom severity at presentation, and Clinical Center.

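### Section 15.3.11 correlates symptom change with Marder change with no baseline term, so initial severity can produce an association even when the degree of lysis has no effect

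*Protocol*

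**What the plan says.** Protocol Section 15.3.11 compares acute symptoms between arms, using analysis of covariance for pain and a t-test for leg circumference. It then adds an analysis within the PCDT arm only: "the mean change scores in leg pain and leg circumference will be correlated with degree of thrombus removal", where removal is taken "as assessed by mean change in Marder scores between pre-PCDT and post-PCDT venograms". It names no covariate for this analysis.

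Four other places bear on it:

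- Section 15.3.9 gives the range of the residual-thrombus measure as a "Marder Score of 0 to 24". It also uses the word correlate, for residual thrombus against PTS, but then says what is meant: "Analysis will include multivariable linear regression for the continuous outcome" and "logistic regression for the binary outcome, adjusting for baseline variables".
- Section 8.11 defines leg pain on a seven-point scale that starts at "1 = No pain, 2 = Very mild pain, 3 = Mild pain".
- Section 15.3 sets the threshold for secondary analyses: "a two-sided p-value of 0.01 or less will be considered statistically significant for all tests".
- Section 15.4.1 lists DVT extent and symptom severity at presentation among its adjustment variables, but its scope is "an adjusted analysis of the study outcomes comparing treatment Arms will be performed using multivariable regression analysis". An association within one arm falls outside it.

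**The concern.** Both variables are changes from a starting value, and each is limited by that value. A patient who starts with a Marder score of 6 can lose at most 6 points, while one who starts at 20 can lose 20. A patient who starts at pain level 3 can fall by 2, while one who starts at 6 can fall by 5. If patients with more clot also tend to start with more pain or swelling, the two changes move together even when the share of clot removed has no bearing on recovery.

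This is the only planned analysis that asks whether removing more clot relieves acute symptoms more. Degree of lysis is not randomised, so a baseline imbalance of this kind has to be handled by the model. An unadjusted positive result could be read as a dose-response when it reflects how severe the DVT was at entry.

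**Working it through.** **Group size.** The protocol gives no figure for this correlation, only for the arm it uses. Section 15.1 states 311 evaluable per arm, for 30% against 20% PTS at 80% power and two-sided 0.05. The normal approximation gives

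n = [1.96·√(2·0.25·0.75) + 0.8416·√(0.30·0.70 + 0.20·0.80)]² / 0.10² = (1.200 + 0.512)² / 0.01, or 294 after rounding up.

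With a continuity correction it is 313, within two patients of 311. Also 311/0.90 = 345.6, which rounds up to the stated 346. I use 311. The number with both venograms and a 10-day or 1-month visit may differ somewhat.

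**Smallest significant correlation.** By Fisher's z, √(311 − 3) = 17.55. At two-sided 0.01 the critical r is tanh(2.576/17.55) = 0.146, so an r that explains about 2% of the variance is enough.

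**Spurious correlation when lysis has no effect.** These inputs are assumptions, not protocol figures:

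- baseline Marder score M: mean 12, SD 5
- fraction lysed f: mean 0.75, SD 0.20, independent of everything else
- baseline pain: mean 4.5, SD 1.2
- follow-up pain: depends only on baseline pain (slope 0.4), residual SD 0.9
- ρ: correlation of baseline Marder score with baseline pain

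Marder change is M·f. Its variance is (0.75² + 0.20²)·25 + 0.20²·144 = 15.06 + 5.76 = 20.82, so its SD is 4.56. Its correlation with the starting score is 0.75·5/4.56 = 0.82.

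Pain change has variance 0.6²·1.2² + 0.9² = 1.328, so its SD is 1.153. Its correlation with starting pain is 0.6·1.2/1.153 = 0.62.

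The induced correlation of the two changes is therefore about ρ·0.82·0.62 = 0.51ρ, before rounding and truncation to the scales.

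**Simulation with rounding and truncation** (3,000 trials per row, n = 311, two-sided 0.01):

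| ρ (assumed) | mean spurious r | raw change on change | adjusted for pre-PCDT Marder and baseline pain |
|---|---|---|---|
| 0 | 0.00 | 0.6% | 1.0% |
| 0.1 | 0.054 | 5.2% | 1.2% |
| 0.2 | 0.110 | 26.8% | 1.0% |
| 0.3 | 0.165 | 64.3% | 1.4% |
| 0.4 | 0.220 | 91.4% | 1.3% |
| 0.5 | 0.275 | 99.3% | 1.4% |

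A hand check at ρ = 0.2: 17.55·atanh(0.110) = 1.94, and P(Z > 2.576 − 1.94) = 26%, which agrees.

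**Sensitivity to the assumptions:**

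- A follow-up slope of 0.7 on baseline pain, or lower and more variable lysis (mean 0.60, SD 0.30), gives about 3% at ρ = 0.1, 14-15% at 0.2 and 35% at 0.3.
- Marder SD 4, lysis 80% (SD 15%) and a baseline-to-follow-up pain correlation of 0.2 to 0.6 give 12-26% at 0.2 and 28-65% at 0.3.
- Calf circumference (assumed limb size SD 4 cm, swelling mean 3 cm, SD 1.5 cm) gives 4.2%, 19% and 50% at 0.1, 0.2 and 0.3.
- Further runs for pain and circumference under other assumed distributions give 4-6%, 18-38% and 49-78%.

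The adjusted regression stayed near 1% in all of these (0.7-1.6%). In the base case, adjusting for the pre-PCDT Marder score alone also restored the nominal rate (0.9-1.2%).

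**The case against.** The strongest reply is that this protocol uses correlate loosely. Section 15.3.9 uses it and then specifies adjusted regression. Section 15.3.10 uses it and points to the multivariate methods of 15.3.8. Section 15.3.11 names no coefficient and does not say unadjusted, and covariates for a secondary association are commonly left to the SAP. Part of this stands: the text does not commit to a Pearson test. But it does fix the outcome as change scores, the exposure as Marder change and the method as correlation, and unlike its neighbours it adds no model or cross-reference. A SAP that follows it literally would run the confounded analysis.

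A second reply is that the link between baseline clot and baseline symptoms is assumed. That is correct. Section 15.4.1 lists both as variables to control but gives no correlation between them. Everyone enrolled has symptomatic proximal DVT of at most 14 days, and how strongly clot extent tracks pain in that group is unknown.

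A third reply is that calf circumference largely reflects limb size, so the room-to-improve argument is less direct than for pain. This is fair, but if clot extent tracks swelling, the inflation is of similar order under the assumptions above.

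Three stronger readings are tempting and go beyond the documents:

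- A reader might infer that a larger clot does drive both changes, so that a false positive is to be expected. At zero baseline correlation there is no inflation.
- A reader might infer that the analysis merely tests initial severity. Marder change contains both starting burden and amount lysed, so the result is confounded by severity and is not a pure measure of it.
- A reader might infer that the result would be used to justify more aggressive clot removal. Nothing in the protocol attaches a decision to it.

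**Conclusion.** The point holds as a weakness in a stated secondary method. It is a free improvement and does not threaten the trial's main conclusions. One link is arithmetic: the starting Marder score limits the Marder drop. The other, that baseline clot and baseline symptoms are related, is an assumption. If it is true even modestly, the false-positive rate rises well above the intended 1%: 3-6% at a baseline correlation of 0.1, 12-38% at 0.2 and 28-78% at 0.3. These ranges also depend on assumed distributions for Marder score, lysis, pain and calf size.

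The spurious coefficient is small, about 0.05 at a baseline correlation of 0.1 and 0.17 at 0.3 in the base case, or under 3% of variance. The harm is therefore a misleading significant result, not a large apparent effect. The primary PTS comparison and the randomised comparisons of pain and circumference are untouched.

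**What to change.** In Section 15.3.11, replace the within-PCDT correlation with linear regression in the PCDT arm:

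- **Outcome:** leg pain, or leg circumference, at 10 days and at 1 month, each fitted separately.
- **Exposure:** change in Marder score from the pre-PCDT to the post-PCDT venogram.
- **Covariates:** the pre-PCDT Marder score and the baseline value of the same symptom.

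Report the coefficient for Marder change with its confidence interval. The section would then match the adjusted approach of 15.3.9. All the variables are already collected, so the cost is a sentence of wording, with no change to visits, sample size or any other analysis.
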